5.5.3.2 Immunological blood collection

Antigen-specific anti-HAAH antibody titers

Anti-HAAH antibody titers from serum samples are determined by ELISA. Patient sera are serially diluted and incubated in microplate wells coated with recombinant HAAH antigen. The plates are then incubated with anti-human immunoglobin G (IgG)-peroxidase conjugate, followed by color development to detect the amount of patient IgG bound to the HAAH antigen. The data are expressed as the reciprocal of the end-point titer.

Antigen-specific CTL responses

Cytotoxic T-cells (CTLs) and APC will be isolated from patient peripheral blood monocytes (PBMCs) by magnetic activated cell sorting (MACS) on the basis of specific cell surface markers. APCs will be loaded with antigen (HAAH) for 3 hours and labeled with a fluorescent dye, carboxyfluorescein succinimidyl ester (CFSE), and incubated with CTLs at varying effector to target cell ratios. Cell-mediated cytotoxicity is determined by antigen-specific release of dye.

Cytotoxic T-Lymphocyte Killing Assay

Quantitation of specific cell lysis by patient-derived CD8+ T-cells will be determined using a flow cytometric assay employing two fluorochromes, 5- (and 6-) carboxyfluorescein diacetate succinimydyl ester (CFSE) and 7-amino actinomycin D (7-AAD). CFSE is pre-loaded into target cells where upon internalization it is covalently linked to intracellular amine groups and thus does not leach from cells into the media nor is it transferred to adjacent cells. As such, CFSE can be used as a marker to differentiate between effector and target cells in the final assay. 7-AAD is a membrane impermeable dye that when added subsequent to the period of cell lysis can only be incorporated only into dead cells (whose membranes have been compromised) and thus can be used to differentiate between live and dead cells.

Target Cells: Patient derived antigen presenting cells (APCs) will be isolated from peripheral blood mononuclear cells (PBMCs) using magnetic assisted cell separation (MACS) technology (Miltenyi Biotec). APCs may be loaded with antigen (HAAH) for 12-16 hrs. prior to use in the CTL assay. Immediately prior to assay, target cells will be loaded with CFSE.

Effector Cells: CD8+ T-cells will be isolated from peripheral blood mononuclear cells (PBMCs) using magnetic assisted cell separation (MACS) technology (Miltenyi Biotec).

Lysis: Effector and target cells will be co-incubated at varying effector to target cell ratios at 37°C for 4 hours. Target cells are held constant at ~25,000 cells per well of a 96 well plate while effector cells will be varied from a ratio of 1:1 with target cells up to 25:1. After incubation, cells are labeled with 7-AAD to differentiate between live and dead cells. Cells are subsequently analyzed by flow cytometry four staining populations are counted: those that stain with both CFSE and 7-AAD, those that stain with CFSE but not 7-AAD, those that stain with 7-AAD but not CFSE and those that do not stain with either fluorophore. Percent specific lysis is determined by taking the ratio CFSE/7-AAD labeled cells to total CFSE labeled cells. The ratio of non-CFSE labeled cells vs. CFSE labeled cells is an indicator of the true effector to target cell ratio.

Measurement of B cell and T cell response

B cells will be isolated from patient PBMCs by magnetic activated cell sorting (MACS) on the basis of specific cell surface markers. After several days of growth in culture, medium will be tested for antigen-specific anti-HAAH antibody titers as above.

CD4+ T-cells responses will be determined by isolating CD4+ T-cells and APC from patient PBMCs by magnetic activated cell sorting (MACS) on the basis of specific cell surface markers. APCs will be loaded with or without antigen (HAAH) for 3 hours and coincubated with CD4+ T-cells overnight. Antigen-specific T-cell activation will be determined by flow cytometric measurement of CD154 and interferon γ .

Measurement of CD4, CD8, CD19 cell populations

CD4+, CD8+ and CD19+ cell populations as a percentage of total PBMCs will be determined by flow cytometry.

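### The protocol's formula for percent specific lysis gives the share of target cells dead from any cause and subtracts no background, so it is not a measure of HAAH-specific killing

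*Protocol*

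**What the plan says.** Protocol 4.2.2 and SAP 6.4 both list antigen-specific CTL responses by dose as a secondary endpoint. Protocol 5.5.3.2 describes the cytotoxicity work twice.

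- **Under the antigen-specific CTL heading.** Antigen-presenting cells (APCs) are loaded with HAAH for 3 hours and labelled with CFSE. The readout is: "Cell-mediated cytotoxicity is determined by antigen-specific release of dye".
- **Under the killing-assay heading.** On loading: "APCs may be loaded with antigen (HAAH) for 12-16 hrs. prior to use in the CTL assay". On the label, CFSE binds inside the cell and "thus does not leach from cells into the media nor is it transferred to adjacent cells"; therefore "CFSE can be used as a marker to differentiate between effector and target cells in the final assay". 7-AAD is added afterwards and enters only cells whose membranes have failed. On the ratios: "effector cells will be varied from a ratio of 1:1 with target cells up to 25:1", with about 25,000 targets per well. The result is defined as: "Percent specific lysis is determined by taking the ratio CFSE/7-AAD labeled cells to total CFSE labeled cells".

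The CD4+ assay in the same section does name an antigen-free comparator: "APCs will be loaded with or without antigen (HAAH) for 3 hours".

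SAP 8.7 (Table 8-1) lists CD8+ IFN-γ under cellular immune response and has no lysis variable. Neither does the list of tables and figures in SAP 10.1. SAP 7.4 sends all collected data to listings, and SAP 8.7 lists all immunologic data.

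**The concern.** A quantity called specific lysis should be near zero when no HAAH-specific killing takes place. The written ratio has no subtraction term, so it also counts targets that died during isolation, loading and the 4-hour incubation, and targets killed by effectors for reasons unrelated to HAAH. Control wells run under a laboratory procedure would not cure this, because the stated formula does not use them.

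What is at stake is the reading of the CTL endpoint. A patient with no HAAH-specific CTLs would show a positive value, and a change in APC viability between visits would look like induction or loss of a response. A difference between dose cohorts could not be attributed to HAAH-specific killing. Cohorts have 3 or 6 patients, so little averaging is available to absorb such shifts.

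**Working it through.** The documents give no numerical target or error rate for this endpoint, so there is no planned figure to reproduce. The check is algebraic.

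**Inputs from Protocol 5.5.3.2.** The numerator is CFSE-positive and 7-AAD-positive cells (dead targets). The denominator is all CFSE-positive cells (all targets). There are about 25,000 targets per well, and effector-to-target ratios run from 1:1 to 25:1.

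**Assumed inputs (none is in the documents).** b = spontaneous target death; u = killing by effectors that does not depend on antigen; s = HAAH-specific killing. Each acts on the targets that survive the others.

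**Formulas.**
- Protocol ratio: R = 1 − (1 − b)(1 − u)(1 − s). This equals s for every s only if b = 0 and u = 0.
- Corrected for target-only wells: C = (R − b)/(1 − b) = 1 − (1 − u)(1 − s).
- For unloaded targets s = 0, so C = u.
- Loaded minus unloaded: D = 1 − (1 − u)(1 − s) − u = s(1 − u).

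| b | u | s | R (protocol) | C, loaded | C, unloaded | D |
|---|---|---|---|---|---|---|
| 10% | 0 | 0 | 10% | 0% | 0% | 0% |
| 20% | 0 | 0 | 20% | 0% | 0% | 0% |
| 30% | 0 | 0 | 30% | 0% | 0% | 0% |
| 10% | 0 | 10% | 19% | 10% | 0% | 10% |
| 20% | 0 | 10% | 28% | 10% | 0% | 10% |
| 30% | 0 | 10% | 37% | 10% | 0% | 10% |
| 10% | 10% | 0 | 19% | 10% | 10% | 0% |
| 30% | 10% | 0 | 37% | 10% | 10% | 0% |
| 10% | 10% | 30% | 43.3% | 37% | 10% | 27% |
| 30% | 10% | 30% | 55.9% | 37% | 10% | 27% |

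Four results follow.

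1. With no specific killing and b of 10% to 30%, the protocol reports 10% to 30% specific lysis, or 2,500 to 7,500 of 25,000 targets.
2. At b = 10%, a patient with s = 10% and u = 0 and a patient with s = 0 and u = 10% both give R = 19%. The formula cannot tell them apart.
3. Target-only wells alone are not enough: with s = 0 and u = 10%, C is still 10%. The unloaded comparison brings it to zero.
4. If b moves from 10% to 20% between two visits with s = u = 0, R rises by 20% − 10% = 10 points and doubles, with no CTL activity at either visit.

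D is zero when s is zero, but it understates s slightly when u is above zero (27% against 30% in the last two rows).

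**The two descriptions side by side.** Loading is 3 hours in one and 12-16 hours in the other. Loading is stated as definite in the first and permissive in the second. The readout is dye release in the first and 7-AAD uptake in CFSE-retaining cells in the second.

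**The case against.** The strongest counter-argument is about reach. A reader might infer that the trial's CTL results by dose will be false. The documents do not support that: no lysis variable appears in SAP Table 8-1 or among the planned tables and figures, so the artefact cannot enter a planned summary. It could reach the listings or a post-hoc analysis, which SAP 7.4 allows. It does not touch the escalation rule in Protocol 5.3.5, which rests on DLTs. Protocol 6.1 mentions immunogenicity alongside DLTs, but gives no rule that uses lysis.

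A reader might also infer that no controls are run. The text shows only that none is stated. The range of ratios is not a plate map, permissive loading could mean that some targets are left unloaded, and SAP 7.4.2 says that immunological results come from the sponsor outside the data-capture system. A laboratory procedure may define controls. This objection stands for the wells but not for the formula, which is explicit and uses no control value. The ratio series could show dependence on effectors, but that is not dependence on antigen, and the formula does not use it either.

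Three further limits stand:

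- The ratio is not death of all cells. Dead effectors carry no CFSE and are excluded.
- The criticised formula sits under the killing-assay heading, while the endpoint shares its name with the other heading. The documents do not say that the second text elaborates the first.
- It would go too far to say that a retained dye can never give a release readout, because the text does not say what happens to CFSE after lysis. If lysed cells do lose it, however, they leave both numerator and denominator of the ratio, which is a further reason to reconcile the two texts.

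**Conclusion.** The point holds as a defect in the protocol's definition. The quantity labelled percent specific lysis is target-cell death from any cause. Under assumed background death of 10% to 30%, it overstates a true value of zero by 10 to 30 percentage points, and a true value of 10% by 9 to 27 points (19% to 37% reported, with u = 0). These sizes rest wholly on the assumed background. That the ratio departs from specific killing whenever background is above zero rests only on the protocol's own definitions.

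The consequence is limited to the protocol-defined CTL endpoint and any lysis values listed or analysed post hoc. It does not affect the planned CD8+ IFN-γ summaries or the MTD and DLT determination. It should be corrected before any lysis result is reported, but it does not threaten the primary objective.

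**What to change.** In Protocol 5.5.3.2:

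1. Include target-only wells and unloaded-target wells, the latter at one prespecified effector-to-target ratio. Require antigen loading in the test wells.
2. Define percent specific lysis = 100 × (experimental % − target-only %)/(100 − target-only %), where each % is 7-AAD-positive cells among CFSE-positive cells.
3. Report the antigen-specific response as loaded minus unloaded at that ratio.
4. For runs already done, apply the correction where control wells exist. Otherwise label the value total target death.
5. Reconcile the two CTL descriptions into one loading time and one readout, and say which of them serves the secondary endpoint.

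**Cost.** A target-only well needs about 25,000 APCs and no effectors. An extra well at 25:1 needs 25 × 25,000 = 625,000 CD8+ cells; at 1:1 it needs 25,000. Repeating the whole ratio series on unloaded targets would double the effector requirement, which is why a single ratio is suggested. Corrected values will be lower and noisier, since each is a difference of measured quantities. If the controls are already run, the change is to wording and calculation only.

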5.5.3.3 Administration site reaction

The area around the administration site will be assessed by the physician for adverse reactions at least 30 minutes post study drug administration. The Investigator will grade any ASRs according to the NCI-CTCAE V4.03 (excluding the actual expected micro-injection punctures).

Patients will be required to report any change in the administration site and return to the clinic for evaluation by the Investigator.

5.5.3.4 ECOG performance score

The health, activity and well-being of the patient was measured by the ECOG performance status and was assessed on a scale of 0 to 5 with 0 being fully active and 5 being dead. Full details are described in Appendix A.

5.5.3.5 Adverse Events (AE)

Adverse event means any untoward medical occurrence associated with the use of a drug in humans, whether or not considered drug related and occurs after the patient is given the first dose of study drug. Any AE that occurs prior to the first dose is part of the medical history.

At least 30 minutes post dose, the Investigator should evaluate the site of drug administration and query the patient in a general manner regarding the presence of any untoward effects.

Laboratory abnormalities (grade 1 and greater that are listed in the NCI-CTCAE V4.03) should be recorded on the AE page regardless of their causality. Worsening of a pre-existing condition is also considered an AE as is the discovery of an abnormal finding during physical exam that was not included in the medical history.

Patients will be encouraged to spontaneously report any AE. Study personnel will ask open-ended questions to obtain information about AEs at every visit. Date and time of onset and resolution (if applicable) of the AE will be documented.

Causality

Events will be considered treatment related if classified by the Investigator as possible, probable, or definitely associated with the use of the drug. Association of events to the study treatment will be made using the following definitions:

| Term | Definition |
|----------------|--|
| Definitely Not | The event is definitely not associated with study treatment. |
| Probably Not | The temporal association, patient history, or clinical condition is such that the study treatment is not likely to have had an association with the observed event. |
| Possible | The event: a) follows a reasonable temporal association with the study treatment administration, but b) could have been produced by the patient's clinical condition or other therapy. |
| Probable | The event: a) follows a reasonable temporal association with the study treatment, b) abates upon discontinuation of study treatment, and c) cannot be reasonably explained by the patient's clinical condition or other therapy. |
| Definite | The event: a) follows a reasonable temporal association with the study treatment, b) abates upon discontinuation of study treatment, c) cannot be reasonably explained by the patient's clinical condition or other therapy, and d) reappears on re-exposure to the study treatment. |

Severity

Signs and symptoms will be graded by the Investigator using the NCI-CTCAE V4.03 graded 1-5. Grade refers to the severity of the AE. For events not described in the NCI CTCAE, the Investigator will assign grades as 1= mild, 2=moderate, 3=severe, 4=life-threatening, and 5=fatal based on this general guideline:

- Grade 1: Mild; asymptomatic or mild symptoms; clinical or diagnostic observations only; intervention not indicated.
- Grade 2: Moderate; minimal, local or noninvasive intervention indicated; limiting ageappropriate instrumental ADL*
- Grade 3: Severe or medically significant but not immediately life-threatening; hospitalization or prolongation of hospitalization indicated; disabling; limiting self-care ADL**.
- Grade 4: Life-threatening consequences; urgent intervention indicated.

Grade 5: Death related to AE. (Grade 5 (Death) may not appropriate for some AEs and therefore may not an option.)

Activities of Daily Living (ADL)

*Instrumental ADL refer to preparing meals, shopping for groceries or clothes, using the telephone, managing money, etc.

**Self-care ADL refer to bathing, dressing and undressing, feeding self, using the toilet, taking medications, and not bedridden.

5.5.3.6 Serious Adverse Event (SAE)

A serious adverse event (SAE) is an AE that:

- Is fatal
- Is life-threatening, meaning the patient was, in the view of the Investigator, at immediate risk of death from the reaction as it occurred, i.e., it does not include a reaction that, had it occurred in a more serious form or progressed, might have caused death
- Is a persistent or significant disability or incapacity or substantial disruption of the ability to conduct normal life functions
- Requires or prolongs inpatient hospitalization
- Is a congenital anomaly or birth defect

Other important medical events may be considered SAEs when, based upon appropriate medical judgment, they may jeopardize the patient and may require medical or surgical intervention to prevent one of the outcomes as listed (# 1-5 above) in this definition.

All SAEs, including death due to any cause, that occur during this study and until 30 days after the last dose of study treatment, whether or not expected and regardless of causality, must be reported to the Medical Monitor immediately upon discovery of the event, using an SAE Form.

The Medical Monitor will advise the Investigator regarding the nature of any further information or documentation that is required. The Investigator should provide the following documentation at the time of notification if available:

- SAE Form
- AE (CRF) page
- Concomitant and support medication pages
- Relevant diagnostic reports
- Relevant laboratory reports
- Admission notes
- Hospital discharge summary (when available).

The Sponsor must notify FDA and all participating Investigators (i.e., all Investigators to whom the Sponsor is providing drug under its INDs or under any Investigator's IND) in an IND safety report of potential serious risks, from clinical trials or any other source, as soon as possible, but in no case later than 15 calendar days after the Sponsor determines that the information qualifies for reporting under paragraph (c)(1)(i), (c)(1)(ii), (c)(1)(ii), or (c)(1)(iv) of 21CFR 312.32. The Sponsor must identify all IND safety reports previously submitted to

FDA concerning a similar suspected adverse reaction, and must analyze the significance of the suspected adverse reaction in light of previous, similar reports or any other relevant information.

Serious and unexpected suspected adverse reaction

The Sponsor must report any suspected adverse reaction that is both serious and unexpected. The Sponsor must report an adverse event as a suspected adverse reaction only if there is evidence to suggest a causal relationship between the drug and the adverse event, such as:

- 1. A single occurrence of an event that is uncommon and known to be strongly associated with drug exposure (e.g., angioedema, hepatic injury, Stevens-Johnson Syndrome);
- 2. One or more occurrences of an event that is not commonly associated with drug exposure, but is otherwise uncommon in the population exposed to the drug (e.g., tendon rupture);
- 3. An aggregate analysis of specific events observed in a clinical trial (such as known consequences of the underlying disease or condition under investigation or other events that commonly occur in the study population independent of drug therapy) that indicates those events occur more frequently in the drug treatment group than in a concurrent or historical control group.

Submission of IND safety reports

The Sponsor must submit each IND safety report in a narrative format or on FDA Form 3500A or in an electronic format that FDA can process, review, and archive. FDA will periodically issue guidance on how to provide the electronic submission (e.g., method of transmission, media, file formats, preparation and organization of files). The Sponsor may submit foreign suspected adverse reactions on a Council for International Organizations of Medical Sciences (CIOMS) I Form instead of a FDA Form 3500A. Reports of overall findings or pooled analyses from published and unpublished in vitro, animal, epidemiological, or clinical studies must be submitted in a narrative format. Each notification to FDA must bear prominent identification of its contents, i.e., "IND Safety Report," and must be transmitted to the review division in the Center for Drug Evaluation and Research or in the Center for Biologics Evaluation and Research that has responsibility for review of the IND. Upon request from FDA, the Sponsor must submit to FDA any additional data or information that the agency deems necessary, as soon as possible, but in no case later than 15 calendar days after receiving the request.

5.5.3.7 Unexpected fatal or life-threatening suspected adverse reaction reports

The Sponsor must also notify FDA of any unexpected fatal or life-threatening suspected adverse reaction as soon as possible but in no case later than 7 calendar days after the Sponsor's initial receipt of the information.

5.5.3.8 Clinical Laboratory Assessments

Hematological toxicities will be assessed in term of hemoglobin value, white blood cell, neutrophil, platelet, and lymphocyte count according to the NCI-CTCAE AE grading.

Laboratory abnormalities (grade 1 and greater that are listed in the NCI-CTCAE V4.03) should be recorded on the AE page regardless of their causality.

5.5.4 Efficacy (Clinical) Measurements

5.5.4.1 PSA assessment

Rising levels of PSA in serum are associated with prostate cancer [9]. Currently, PSA testing of serum is a standard test for indicating further investigation for prostate cancer.

A cutoff of 4.0 ng/mL has a sensitivity of 67.5-80% for detecting prostate cancer [10].

5.5.4.2 Treatment Failure

Treatment failure will be assessed by the observance of PSA doubling less than 90 days or unacceptable toxicity as determined by the Investigator.

5.6 Data Quality Assurance

At the study sites, all CRFs will be manually reviewed for completeness by the Sponsor's Clinical Research Associates. Site Staff will enter the required subject data into the provided Code of Federal Regulations (CFR) Part 11-compliant electronic data capture (EDC) system. Programmed computer edit checks will be run against the database to check for discrepancies and plausibility of the data. All issues resulting from the computer-generated checks will be resolved according to the Sponsor's standard data management practices in conjunction with the medical monitor, clinical study personnel, and the study Investigators.

6. Statistical Methods and Determination of Sample Size

6.1 Statistical and Analytical Plans

No formal statistical analysis will be performed, however, statistical derivation of all data will be derived by dose cohort and displayed for inspection.

For the dose-escalation phase of the study, cohorts of 3 or 6 patients will be screened, registered and treated at each dose level. The actual sample size may vary depending on the incidence of DLT during Cycle 1 at a given dose level. Once the MTD/RP2D is determined, additional patients may be accrued to provide for 6 patients in the MTD cohort. Approximately, 18 patients will be screened, registered and treated in the trial.

The primary safety analysis will assess MTD and AEs, clinical laboratory tests, and tolerability, based on the combined evaluation of immunogenicity and incidence of DLTs in each patient.

